6.4.2 Notifications

6.4.2.1 Notifications by the Investigator to CCTU

CCTU must be notified of all SAEs excepting those listed in 6.1.2.1 - unless considered **causally related** to the intervention immediately after site staff become aware of the event (in no circumstances should this notification take longer than 24 hours).

The Foreseeable (expected) SAEs listed in section 6.1.2.1 must be reported within 24 hours of site staff becoming aware of them **if they are considered causally related** to the trial intervention (NEL).

'Foreseeable SAEs' that are **not considered causally related** to the trial intervention (NEL) should be reported within 5 working days using the SAE report form.

All 'Unforeseeable SAEs' i.e., all other SAEs occurring in trial participants which are not detailed in Section 6.1.2.1 should be reported within 24 hours of site staff becoming aware of them using the SAE report form.

All Notifiable AEs (NAEs) listed in Section 6.2 should be reported within 5 working days using the Notifiable Adverse Events (NAE) CRF.

Investigators should notify CCTU of any SAEs and Notifiable Adverse Events (NAEs) occurring from the time of randomisation until 2-year hospital visit follow up. From this point forward the site will not actively monitor SAEs or NAEs.

The SAE form must be completed by the site staff named on the delegation log with this responsibility assigned by the PI. The form should be reviewed and signed off by the investigator (listed on the delegation log) who is responsible for the participant's care with

attention paid to the grading and causality of the event. The responsible investigator should check the SAE form at the earliest opportunity, make any changes necessary and sign. Systems should be in place at the site to enable the investigator to check the form for clinical accuracy as soon as possible.

The minimum criteria required for reporting an SAE are the primary event term, participant's trial specific PIN, date of birth, name of reporting investigator and sufficient information on the event to confirm seriousness. Any further information regarding the event that is unavailable at the time of the first report should be completed as soon as it becomes available.

Follow-up: Participants must be followed up until clinical recovery is complete, laboratory results have returned to normal or baseline values, or until the event has stabilised. Follow-up should continue after completion of 2-year trial follow-up if necessary. If there are ongoing SAEs at the study end this should be discussed with TMG. Follow-up SAE forms should be completed as further information becomes available. Additional information and/or copies of test results etc may be provided separately. The participant must be identified by trial specific PIN, date of birth and initials only. The participant's name should not be used on any correspondence and should be blacked out and replaced with trial identifiers on any test results.

SAE REPORTING (For all causally related Foreseeable and all Unforeseeable SAEs)

Within 24 hours of investigator becoming aware of an SAE:
The SAE must be entered on to the sponsor's central database and the trial team
at CCTU notified at [contact]

6.4.2.2 UCL CCTU responsibilities

Clinical reviewer (Chief Investigator, or a medically qualified delegate) will review all SAE reports received. The causality assessment given by the local investigator at the hospital cannot be overruled; in the case of disagreement, both opinions will be provided in any subsequent reports.

The clinical reviewer will complete the assessment of expectedness using table 6 (NEL risks and mitigations) in **section 6.3.1.5.**

CCTU is undertaking the duties of trial sponsor and is responsible for the reporting of SAEs occurring to research participant where in the opinion of the clinical reviewer the event was related and unexpected, to the REC within 15 days of the sponsor becoming aware of the event.

CCTU will keep investigators and the IDMC informed of any safety issues that arise during the course of the trial.

In the UK, an Annual Progress Report (APR) will be submitted to the REC within 30 days of the anniversary date on which the favourable opinion was given, and annually until the trial is declared ended.

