6.4.1.3 Causality

The investigator must assess the causality of all serious events in relation to the intervention (NEL) using the definitions in Table 5.

Table 5: Causality Definitions

Relationship	Description
Unrelated	There is no evidence of any causal relationship
Related	There is clear evidence to suggest a causal relationship to the intervention and other possible contributing factors can be ruled out

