6.4.1.4 Expectedness

If there is at least a possible involvement of the trial intervention (NEL), the sponsor will assess the expectedness of the event. If information of expectedness is provided by the investigator this should be taken into consideration by the sponsor. An unexpected adverse event is one not reported in Table 6 NEL Risks and mitigations (**Section 6.3.1.5**).

6..1.5 Risks associated with NEL

The risks associated with NEL for the ENLIVEN-UK trial are listed in Table 6 (NEL risks and mitigations) below:

Table 6. NEL risks and mitigations.

POTENTIAL RISK	RISK MANAGEMENT
Infection	Procedure in strict sterile conditions in operating theatre as per standard practice. Peri-operative antibiotics are given and the choice of agent and duration will vary according to local guidelines.
Secondary bleeding	There is a clear consensus on surgical protocol to ensure maximal safe washout without causing secondary bleeding in the ventricles or in the brain. The surgeon should stop when they feel they have achieved a 'maximal safe washout' as defined in the consensus guideline (28).
Stroke	Procedure-related brain injury risk has not been reported with NEL and therefore, the

	risk is low. It will be identified if it occurs on
	the post-operative ultrasound scan.
CSF leak	Standard closure techniques will be used to
	protect against CSF leak and, if it develops,
	will be managed at the discretion of the
	treating surgeon.
Seizures	Seizures (up to CTCAE Grade 3) can arise
	as a result of the initial IVH or procedure-
	related brain injury. These have been
	reported with NEL but the risk is low. If it
	occurs, it will be managed at the discretion of
	the treating medical team including
	neurosurgeon and neonatologist.
Temporising device dysfunction	The TD may stop working adequately due to
	either blockage, insufficient drainage or
	infection. At this stage, the clinical team will
	make an assessment as to whether it needs
	to be revised or whether a permanent
	ventriculoperitoneal shunt needs to be
	placed. This management will remain at the
Flootrolyte/Codings imbalance	discretion of the treating neurosurgical team.
Electrolyte/Sodium imbalance	The use of irrigating solution may lead to
	disturbances in the serum level of sodium
	and other electrolytes. This will be mitigated
	by using appropriate irrigating solutions, such
	as Ringer Lactate or artificial CSF and by
	monitoring electrolyte levels in the serum as

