6.5 Safety Monitoring

The Independent Data Monitoring Committee (IDMC) will review the study data and outcomes including SAEs. All infant deaths will be reported to the IDMC promptly, as and when they are reported to CCTU, to review on a case-by-case basis. The IDMC will ensure the safety and wellbeing of the trial participants and, if appropriate, make recommendations to the Trial Steering Committee (TSC) regarding continuance of the study or modification of the Protocol. The TSC will have ultimate responsibility for deciding whether the trial should be stopped on safety grounds.

CCTU will also provide safety information to the Trial Management Group on a periodic basis. Notifiable events including CSF infections will be monitored closely and reviewed at TMG meetings.

Trial Intervention (NEL) compliance:

Non-compliance with the intervention (NEL) is not anticipated but trial data will be reviewed on a monthly basis and post-operative ultrasound scans, will be reviewed at least quarterly by the TMG to evaluate any variability in the surgical procedures.

Where necessary, feedback will be given to the PI at the participating site regarding their operative technique and radiographic outcome. Any relevant issues will be discussed with the participating unit.

7 Quality Assurance & Control

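### Section 6.4.2.2 protects the site's causality rating but lets the clinical reviewer's opinion alone decide whether the 15-day ethics report is due

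*Protocol*

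**What the plan says.** Section 6.4.1.3 gives the causality judgement to the site: "The investigator must assess the causality of all serious events in relation to the intervention (NEL) using the definitions in Table 5". Table 5 has two categories, Unrelated and Related. Related requires that "There is clear evidence to suggest a causal relationship to the intervention and other possible contributing factors can be ruled out".

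Section 6.4.2.2 adds a central review: "Clinical reviewer (Chief Investigator, or a medically qualified delegate) will review all SAE reports received". On causality it states "The causality assessment given by the local investigator at the hospital cannot be overruled" and continues that "in the case of disagreement, both opinions will be provided in any subsequent reports". It then assigns the expectedness assessment to the clinical reviewer, using Table 6.

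The duty to report to the REC comes next in the same section. CCTU, acting for the sponsor, reports SAEs "where in the opinion of the clinical reviewer the event was related and unexpected, to the REC within 15 days" of the sponsor becoming aware. Both conditions, relatedness and unexpectedness, are tied to the clinical reviewer's opinion.

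**The concern.** The section makes two statements about whose view of causality counts, and they part company in the one situation where it matters: the site says Related and the clinical reviewer says Unrelated. The protecting sentence says the site's view stands. The reporting sentence takes no account of it. If the reporting sentence is followed, the clinical reviewer's view decides the outcome on the expedited route, which is overruling in effect.

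At stake is the REC's prompt notice of an event that a treating site has attributed to NEL and that is not among its listed risks. Under Table 5 a site rating of Related already meets a demanding standard, so it is not a casual signal. Disagreement is plausible: Section 4.4 describes infants at risk of many medical problems, and Section 6.1.1 anticipates a high incidence of adverse events during the hospital stay.

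**Working it through.** No calculation applies. The check sets the reporting rule beside the causality rule and works through every combination of opinions.

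**Inputs**
- Who rates causality for all serious events: the site investigator (Section 6.4.1.3).
- Status of that rating: it cannot be overruled (Section 6.4.2.2).
- Handling of disagreement: both opinions go into any later report (Section 6.4.2.2).
- REC trigger: related and unexpected in the clinical reviewer's opinion, 15 days (Section 6.4.2.2).
- Meaning of unexpected: not among the risks in Table 6 (Section 6.4.1.4).

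**Step 1. The four cases, for an SAE assessed as unexpected**

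| Site rating | Clinical reviewer's rating | 15-day REC report under the literal text |
|---|---|---|
| Related | Related | Due |
| Unrelated | Related | Due |
| Unrelated | Unrelated | Not due |
| Related | Unrelated | Not due |

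The result follows the clinical reviewer's column in every row; the site's column never changes it. The last row is the conflict: the site's Related rating is said to stand, yet it has no consequence on this route.

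**Step 2. Does the both-opinions provision repair the last row?** It does not. It says what a report must contain once there is one, and does not itself require a report. In the last row no expedited report is triggered, so on that route there is nothing to carry the two opinions.

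**Step 3. What still happens to an event in the last row?**
- It reaches CCTU within 24 hours. Section 6.4.2.1 sets that limit for all unforeseeable SAEs and for foreseeable ones considered causally related to NEL, so an SAE the site rates related is covered whichever list it falls under.
- Section 6.5 states: "The Independent Data Monitoring Committee (IDMC) will review the study data and outcomes including SAEs". This does not depend on the clinical reviewer's opinion.
- An annual progress report goes to the REC (Section 6.4.2.2), and any urgent safety measure is notified to the REC within 3 days (Section 6.4.2.3).

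**Step 4. Do these routes replace the 15-day report?** Not fully. Section 6.5 promises prompt case-by-case notice to the IDMC only for deaths, and Section 13.3 leaves its meeting frequency to its terms of reference. The protocol does not say how the annual report treats disputed SAEs. The urgent-measures notice applies only if such measures are taken. None of them gives the REC the disputed event within 15 days as a matter of rule.

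**The case against.** The strongest reply is that the section can be read consistently. The sentence protecting the site's rating is categorical, and the next paragraph gives the clinical reviewer expectedness. On that reading a site's Related rating stands, the clinical reviewer decides only whether the event is expected, and the report carries both views. The reporting sentence would then be loose drafting. This may well be what was intended, and nothing in the protocol shows an intended veto. But the reporting sentence ties relatedness as well as unexpectedness to the clinical reviewer's opinion. The two readings give opposite answers in the last row of the table, and staff applying the section cannot tell which one holds.

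A reader might also infer more than the protocol supports:

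- *That disputed events go unreported altogether.* They do not. They reach CCTU within 24 hours, SAEs go before the IDMC, and disputes in the other direction do trigger the REC report.
- *That the number lost can be gauged from the complication risks of less than 5% in Section 1.4.* Those risks (infection, haemorrhage, seizures, CSF leak, electrolyte disturbance, brain injury) are largely the ones in Table 6, which makes them expected and so outside the 15-day rule whoever judges causality. They say nothing about how often a related and unexpected SAE will occur or be disputed.
- *That Section 6.4.1.4 sets a rival, lower trigger.* Its sentence, "If there is at least a possible involvement of the trial intervention (NEL), the sponsor will assess the expectedness of the event", starts the expectedness assessment. It does not trigger a REC report.
- *That the clinical reviewer would be judging events from their own unit.* The protocol does not list the sites and allows a delegate, so this is speculation.

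**Conclusion.** Wrong as written. Section 6.4.2.2 contradicts itself on whether the site's causality rating can be set aside for expedited reporting. The consequence is confined to one class of event: an SAE that is unexpected against Table 6, rated related by the site and unrelated by the clinical reviewer. For that class the literal text requires no 15-day report to the REC, although the event is still known to CCTU within 24 hours and falls within IDMC review. The protocol gives no rate for such events, so their number cannot be estimated; it may be small or nil.

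The conclusion assumes that the reporting sentence is applied as worded. If the intention was that a site's Related rating suffices, practice may already be sound, but the text should say so. This is a safety-reporting rule set by the protocol itself, and it does not affect the statistical analysis.

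**What to change.** Reconcile the two statements by rewording the REC trigger in Section 6.4.2.2 along these lines:

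> CCTU will report to the REC within 15 days any SAE that either the local investigator or the clinical reviewer considers related to the intervention and that is assessed as unexpected; where they disagree, both opinions are included.

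This changes only the last row of the table, from not due to due. The clinical reviewer keeps the expectedness assessment against Table 6, and the both-opinions provision then has a report to act on. The cost is a one-sentence protocol change, a matching line in the safety procedure, and possibly a few more reports to the REC. No clinical management changes.

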6.4.2.3 Urgent Safety Measures

The CCTU or investigator may take appropriate urgent safety measures in order to protect research participants against any immediate hazard to their health or safety.

In the UK, if any urgent safety measures are taken the CCTU shall immediately (no later than 3 days from the date the measures are taken), give written notice to the REC of the measures taken and the circumstances giving rise to those measures, according to the relevant CCTU SOP.

6.5 Safety Monitoring

The Independent Data Monitoring Committee (IDMC) will review the study data and outcomes including SAEs. All infant deaths will be reported to the IDMC promptly, as and when they are reported to CCTU, to review on a case-by-case basis. The IDMC will ensure the safety and wellbeing of the trial participants and, if appropriate, make recommendations to the Trial Steering Committee (TSC) regarding continuance of the study or modification of the Protocol. The TSC will have ultimate responsibility for deciding whether the trial should be stopped on safety grounds.

CCTU will also provide safety information to the Trial Management Group on a periodic basis. Notifiable events including CSF infections will be monitored closely and reviewed at TMG meetings.

Trial Intervention (NEL) compliance:

Non-compliance with the intervention (NEL) is not anticipated but trial data will be reviewed on a monthly basis and post-operative ultrasound scans, will be reviewed at least quarterly by the TMG to evaluate any variability in the surgical procedures.

Where necessary, feedback will be given to the PI at the participating site regarding their operative technique and radiographic outcome. Any relevant issues will be discussed with the participating unit.

7 Quality Assurance & Control

7.1 Risk Assessment

The Quality Assurance (QA) and Quality Control (QC) considerations for the ENLIVEN-UK trial are based on the standard CCTU Quality Management Policy that includes a formal Risk Assessment, and that acknowledges the risks associated with the conduct of the trial and proposals of how to mitigate them through appropriate QA and QC processes. Risks are defined in terms of their impact on the rights and safety of participants; project concept including trial design, reliability of results and institutional risk; project management; benefit risk of the trial (see section 1.4); and other considerations.

QA is defined as all the planned and systematic actions established to ensure the trial is performed and data generated, documented and/or recorded and reported in compliance with the principles of GCP and applicable regulatory requirements. QC includes the operational techniques and activities performed within the QA system to verify that the requirements for quality of the trial related activities are fulfilled.

The ENLIVEN-UK Risk Assessment has been reviewed by the CCTU's Quality Management Group (QMG).

7.2 Central Monitoring at CCTU

CCTU staff will review data and other information provided by investigators to identify trends, outliers, anomalies, protocol deviations and inconsistencies. The frequency and type of central monitoring will be detailed in the ENLIVEN-UK Quality Management and Monitoring Plan (QMMP).

7.3 Monitoring

The frequency, type and intensity of routine on-site monitoring and the requirements for triggered on-site monitoring will be detailed in the ENLIVEN-UK QMMP, including any provision for remote or self-monitoring. The QMMP will detail the procedures for review and sign-off of monitoring reports. In the event of a request for a trial site inspection by any regulatory authority UCL CCTU must be notified as soon as possible.

7.3.1 Direct access to Participant Records

Participating investigators must agree to allow trial-related monitoring, including audits, EC review and regulatory inspections, by providing access to source data and other documents as required. Participant consent for this must be obtained as part of the informed consent process for the trial.

7.3.2 Confidentiality

CCTU plan to follow the principles of the UK DPA regardless of the countries where the trial is being conducted.

Participant's data will be collected and kept securely. Confidentiality of participant's personal data is ensured by not collecting participant names and other personally identifiable information on CRFs and receiving only pseudonymised data. At the time of consent, participants will be allocated a Participant Identification Number (PIN), which will be used on all trial related paperwork sent to UCL CCTU and in the trial database.

Any documents (e.g., screening and enrolment logs) linking trial specific PIN to participant's personally identifiable information will be kept securely at site; only redacted copies will be sent to Sponsor if requested.

Copies of participant's trial data will be kept at the participating site in a secure location with restricted access. Unless working at a site, CCTU staff will only have access to the data collected on the trial CRFs (i.e., they will not have access to any other personal data) and applicable source data, moreover only staff working on the trial will have access to these data. Data stored electronically are held on secure servers, that have restricted access.

The informed consent form will carry the participant's name and an appropriate signature; these will be retained at the trial site (participant's hospital). The consent forms will only be accessed by UCL CCTU staff for purposes of monitoring the consent procedure at the site. Trial-specific samples will be labelled 'ENLIVEN-UK', with the trial specific participant PIN, visit name and date of birth.

7.4 Source Data

The investigator/institution should maintain adequate and accurate source documents and trial records that include all pertinent observations on each of the site's trial participants. Source data are contained in source documents and are defined by EU guidelines as all information in original records that are used for the reconstruction and evaluation of the clinical trial. Source documents are the first place where the source data are recorded. These can include hospital records, clinical and office charts, surgical and laboratory notes, scans and source data worksheets.

Source data should be attributable, legible, contemporaneous, original, accurate, and complete. Changes to source data should be traceable, should not obscure the original entry, and should be explained if necessary (e.g., via an audit trail). Each data element should only have one source.

For this trial the CRFs/eCRFs will not be the source document for any data elements.

The following data should all be verifiable from source documents, which may include paper notes and electronic health records:

- signed consent forms
- dates of visits including dates any trial specimens were taken and processed in the laboratory
- eligibility and baseline values
- adverse events of any grade that lead to treatment modification and adverse events judged as related to the intervention
- Serious adverse events Foreseeable SAEs, Unforeseeable SAEs and Notifiable AEs (please refer to section 6.1 for definitions)
- Ultrasound and MRI scans*
- Bayley Scales of Infant and Toddler Development (4th edition) (Bayley IV)

- Adapted Client Service Report Inventory (CSRI) Children version
- Quantitative Checklist for Autism in Toddlers (Q-CHAT)
- Brief Infant Toddler Social Emotional Assessment (BITSEA)
- TNO-AZL TAPQOL Preschool Children's Quality of Life Questionnaire
- EuroQoL EQ-5D-5L Questionnaire

*Ultrasound and MRI scans will be transferred to University College London (UCL) and then uploaded to the Data Safe Haven facility at UCL. Please refer to the Imaging Transfer Guidelines for further details.

Paper CRFs (pCRFs) will be provided to the site to be used as a back-up for instances when the EDC is unavailable (e.g., system updates, build maintenance, system failures). pCRFs will be provided to sites and should only be used as a temporary measure until the EDC is restored.

A Source Data Agreement will be put in place as part of the site activation process with each site. This will define the source documents and the data therein, together with location of these source documents and any applicable plans for transmission of source data between the site and CCTU.

